This project is not collaborative with another entity/institution/outside investigator. VA is the only institution, and all PIs/personnel are affiliated with and appointed by the VA. This is an RLR Indy VA Veteran participant only (identified via VA CDW), single VA personnel only, and VA HSRD salary supported study utilizing VA approved technology systems for/such as: VA encrypted Azure email, VA audio visual platform, VA approved recording devices, VA medical record access, with VA data collection tools and data analysis tools within the VA network and stored only on the VA network. All visits occur virtually.

1.0 Background

Community reintegration is a critical period of transition for post-9/11 Veterans that is rife with challenges.¹⁻³ Separating from military service and reintegrating into civilian life is often characterized by a range of psychosocial stressors and adjustment difficulties, such as social isolation and challenges establishing a new personal identity.^{4,5} Reintegration

becomes further complicated if the Veteran is returning to civilian life with a service-related condition.^{1,6} Of particular concern is depression, which is one of the most costly and common mental health diagnoses among the post-9/11 Veteran cohort.^{7,8} Prior research has demonstrated that depression is strongly associated with poor psychosocial outcomes and reintegration challenges among Veterans.^{6,8} Successful community reintegration requires programming that effectively promotes and addresses post-9/11 Veterans' mental health needs, particularly depression.²

2.0 Rationale and Specific Aims

If not properly addressed, Veterans' reintegration challenges can place a tremendous burden on Veterans, their families, communities, and healthcare systems.⁹⁻¹¹ Despite the well-documented needs of post-9/11 Veterans and numerous resources, Veterans continue to report inadequate support for the transition from military to civilian life.^{4,10,12-16} Moreover, many Veterans do not use available services.^{17,18} As such, reintegration services must address Veterans' mental health care needs using approaches that increase the likelihood of Veteran engagement. Mindfulness-based reintegration services are a promising approach for reducing post-9/11 Veterans' symptoms of depression and are supported by previous research that demonstrates (1) beneficial effects of mindfulness meditation in reducing depression;¹⁹⁻²² (2) the potential of mindfulness to mitigate self-stigma, which is a key barrier to seeking mental health care among Veterans;^{18,23} and (3) Veterans' interest in the use of mindfulness to help manage depression.²⁴⁻²⁶ The appeal of mindfulness-based reintegration services may be further enhanced by virtual delivery.²⁴

The overarching goal of the proposed project is to use mindfulness practices to reduce depression and improve community reintegration among post-9/11 Veterans. This proposal focuses on the REconnecting to Civilian Life using Activities that Improve Mindfulness (RECLAIM) intervention. RECLAIM is a virtual multi-component, mindfulness-based intervention developed by our study team in collaboration with VA clinicians, post-9/11 Veterans, and stakeholders and guided by the VA Whole Health framework.^{27,28} The proposed project builds on preliminary pilot work and a Small Award Initiative for Impact (SWIFT) pilot project funded by our VA HSR&D Center of Innovation. In the SWIFT pilot, we refined the RECLAIM content and tested the feasibility of virtual delivery with a small sample (N=18) using a single arm pre/post-test design. The proposed pilot project builds on preliminary work by (1) testing the refined intervention in a randomized controlled design to assess feasibility of recruitment for a randomized trial, (2) randomization, (3) retention in both study arms, and (4) intervention acceptability. Findings from the proposed project will support a HSR&D Investigator Initiated Research Merit award application that will assess the effectiveness of RECLAIM while simultaneously planning for implementation in a Hybrid Type I trial.²⁹ The following are the specific aims for this pilot project.

Aim 1: Conduct a randomized controlled pilot study to assess feasibility of the RECLAIM intervention. We will conduct a two-arm randomized pilot study. Veterans (N=48) will be randomized to either the intervention arm (i.e., virtually delivered RECLAIM) or a control arm (i.e., psychoeducation materials). We will assess intervention feasibility, including recruitment, randomization, administration and completion of outcome assessments, treatment engagement, and retention in both the intervention and control study arms.

Aim 2: Conduct qualitative interviews to assess acceptability of RECLAIM. A purposefully sampled subgroup (i.e., based on attendance) of RECLAIM participants (i.e., Veterans from the intervention arm; N=16) will engage in a qualitative interview to explore experiences in RECLAIM, including perceived strengths and suggestions for future improvements.

Aim 3: Refine and finalize the RECLAIM intervention. As findings emerge from the Aim 1 pilot test and Aim 2 interviews with Veteran participants, we will iteratively update the RECLAIM protocol manual and testing procedures (i.e., randomization, control group materials). We will consult with the Patient Advisory Council of the Indianapolis VAMC to gather Veteran feedback on the revised RECLAIM protocol manual, as well as partners (e.g., Patient Centered Care and Cultural Transformation). These actions will help refine the study methods, design, and intervention in anticipation of a larger trial.

3.0 Study Plan, Experimental Design, and Methodology

Aim 1: We will conduct a two-arm randomized controlled pilot study to assess feasibility of (1) recruitment using VA electronic medical record data (in contrast to primarily networking and word of mouth in our preliminary pilot study), (2) the randomization strategy, (3) retention in both study arms, (4) participant engagement in the intervention, and (5) outcome assessment administration (e.g., time to complete, proportion completed, attrition).

Aim 2: We will conduct qualitative interviews with Aim 1 pilot study participants who were randomized to the RECLAIM arm. We will use principles of rapid analysis to analyze the qualitative data.^{30,31}

Aim 3: Consistent with the intervention mapping approach³² used to design RECLAIM, as findings emerge from this project - the Aim 1 pilot test and Aim 2 interviews with Veteran participants - we will iteratively update RECLAIM content in the protocol manual. Intervention protocol manuals are necessary to facilitate rigorous and systematic evaluation of interventions and are useful for translating effective intervention strategies across settings.³³ We will also refine the procedures for testing the RECLAIM intervention (e.g., recruitment strategies, control group materials).

4.0 Inclusion/Exclusion Criteria

To be eligible for this study, Veterans must be between the ages of 18 and 44. Majority of post-9/11 Veterans fall into this age range, as do the highest rates of depression in this Veteran cohort.^{34,35} Veterans must have also served (a) active duty and/or (b) in the National Guard/Reserves after October 2001. Potential participants can still be in the National Guard or a Reservist. Veterans must be enrolled in VHA care. Veterans must also endorse at least a mild level of depression. We will use the Patient Health Questionnaire (PHQ-9)³⁶ to assess the presence and severity of depressive symptoms among potential Veteran participants. Mild depression is defined as a score of at least 5 on the PHQ-9. Finally, Veterans must also endorse at least a little difficulty adjusting to civilian life to be eligible for participation. Difficulty adjusting to civilian life will be assessed using the Military to Civilian Questionnaire (M2C-Q).³⁷ For this study, "a little" difficulty will be defined as a mean M2C-Q score of 1 (i.e., a 1 indicates "a little difficulty" on the M2C-Q).

Mental health screening: As previously mentioned, we will use the Patient Health Questionnaire³⁶ (PHQ-9) to screen participants for depressive symptoms. Veterans who present with a score of 20 or greater (i.e., severe depression) or endorse the 9th item (i.e., suicidal ideation) on the PHQ-9 will then complete the Columbia Suicide Severity Rating Scale (C-SSRS)³⁹ to determine if the Veteran is currently experiencing suicidal ideation and needs further evaluation by a VA provider. Veterans will not be immediately excluded from participation in the study; the study team will consult with the Roudebush Suicide Prevention Team and/or the Veterans' care provider to determine whether continued study participation is appropriate. If a Veteran is experiencing active suicidal ideation, the following steps, aligned with the Indianapolis VAMC policy (116-05), will be taken: Veterans who are experiencing active suicidal ideation will be immediately connected to the Veterans Crisis Line. If the warm transfer to the Veterans Crisis Line fails, the study team member will attempt to call the Veteran back immediately. If the Veteran cannot be located, then the study team member will call the Veterans Crisis Line to provide them with the Veteran's information and receive guidance on next steps. If the Veterans Crisis Line decides not to pursue follow up to locate a Veteran caller, the study team member will then contact the local suicide prevention team (i.e., the team located at the facility that the patient is receiving healthcare services). In either of these scenarios, the Suicide Prevention Team will initiate suicide risk management protocol, documentation, and follow up plans. The complete protocol for screening and referring Veterans needing additional care was developed in collaboration with the Roudebush Suicide Prevention Team). Screening measures will be collected prior to the baseline assessment and collected during each outcome assessment.

5.0 Recruitment/Enrollment/Randomization

Under an IRB approved HIPAA Authorization Waiver for recruitment, we will request a list of Veterans and their contact information based on the study inclusion criteria (e.g., age and service area) via CDW. Eligibility criteria included in this CDW request will also seek a depression diagnosis, but participation is not solely contingent upon any health conditions (i.e., potential participants may still present mild depression symptoms without a formal depression diagnosis). The research assistant will mail a recruitment brochure and letter to eligible Veterans. Study staff will then contact these eligible Veteran participants (who were initially contacted by mail) by phone and/or email to recruit them for the study. Veterans who enroll will be emailed using VA compliant methods (VA Azure encrypted email). Word-of-mouth and snowballing techniques will also be used to identify eligible Veteran participants.

Other methods of study referral: Preliminary work for the RECLAIM intervention established a network of VA staff and providers and VA stakeholders (e.g., [name], M2VA Case Management program) who are willing to refer Veterans to the study. During recruitment, to ensure the representation of minoritized and women Veterans, we will contact the Minority Veterans Program and the Women's Clinic to discuss the proposed project and ask for staff and clinician assistance for study referral. Finally, participants will be recruited through word-of-mouth and snowballing techniques.

Recruitment and retention strategies: Based on findings in our preliminary studies,²⁷ the following strategies will be used to maximize recruitment and retention: (1) Use recruitment and program materials with clear and transparent messaging (based on preliminary findings from Veterans to avoid vague language); (2) Gather multiple forms of contact information; (3) Establish Veterans' preferred contact method (email or phone) and contact time preferences (e.g., morning or evening); (4) Offer incentives for outcome assessments and interviews; (5) Send recap emails following sessions that contain overviews of session topics and discussion, and a reminder for the upcoming session; (6) Reminder call day of RECLAIM session.

If target recruitment numbers are not being met, we will (1) consult with our operational and clinical partners (e.g., Office of Mental Health and Suicide Prevention; [name], Military2VA Case Management program) for suggestions on identifying potential participants; (2) call and send letters to VA staff and providers and community-based Veteran service organizations to explain the study and ask for referrals; (3) present information about the study and preliminary findings to VA staff and providers and local organizations; (4) follow up with VA staff and providers and organizations who referred Veterans to the study to capitalize on good sources of referrals; and (5) use VA-approved social media to recruit Veterans.

6.0 Study Procedures

Aim 1 Procedures

Veterans who consent to participate in the pilot study will complete the eligibility screening over the phone or using VA-approved teleconferencing software. Eligible Veterans must (1) be between the ages of 18 and 44, (2) have served active duty and/or in the National Guard/Reserves after October 2001, (3) endorse a mild level of depression (i.e., at least a score of 10 on the PHQ-9, and (4) at least some difficulty with their community reintegration (i.e., a mean M2C-Q score of 2). Veterans will receive a copy of the consent form, which will include information such as potential risk and benefits and contact information if issues should arise. A request to VA ORD (Office Research Development) will be made and ORD permission provided, under VA's contracted use of DocuSign, to allow participants to sign the HIPAA Authorization electronically with DocuSign envelopes. Eligible Veterans will also complete baseline outcome assessments. These assessments will be completed again at the 2-month follow-up. **Randomization:** After completing the informed consent and baseline assessments, Veteran participants will be randomized to one of two study arms: (1) virtually delivered RECLAIM arm, or (2) the control arm. Randomization will occur using the block randomization method, which balances the number of participants in each study group across time.

Intervention arm: Veterans randomized to the intervention arm (n=24) will participate in the 8-week RECLAIM intervention after 12 Veterans (i.e., a cohort) have been randomized. **Delivery of RECLAIM:** The RECLAIM intervention is comprised of (1) four 60-minute sessions that are delivered bi-weekly in a virtual group setting and (2) four bi-weekly coaching calls. Participants will also be offered an introductory session (i.e., Session 0) that will serve as a technical assistance session to ensure that participants can access Microsoft Teams and to try and mitigate connection challenges prior to the start of the intervention. The bi-weekly coaching calls will happen in the weeks between the virtual intervention sessions. Delivery of the bi-weekly intervention virtual sessions will be led by [name], who is a study consultant and an expert in mindfulness (e.g., certified as a Mindfulness Based Meditation for Pain Relief practitioner) and co-facilitated by [name]. Each RECLAIM session is structured with the following components to achieve this purpose: (1) an overview and discussion of the weekly topic, which is a domain of community reintegration; (2) a brief mindfulness practice (approximately 10 minutes); (3) reflection and discussion of the topic and mindfulness practice; (4) journal prompt and brief discussion; and (5) a discussion of ways to effectively engage in independent mindfulness practice(s). RECLAIM participants will be invited, but not required, to participate in optional check-in sessions which will occur between the regularly scheduled weekly RECLAIM sessions. The bi-weekly coaching calls will be conducted by the project manager ([name]) or [name].

Control arm: The inclusion of a control group in the proposed pilot project will allow us to test aspects of and procedures for the control group in preparation for the larger scale study.⁴⁰ We will also assess feedback from the control arm participants to determine whether our approach is feasible for inclusion in a future fully powered randomized controlled trial (RCT). We will use an attention control group design. Participants in the control arm will not receive the RECLAIM intervention but will receive some similar RECLAIM activities. They will not be the same in intensity, time, and/or contacts as the intervention activities.⁴¹ We will provide Veterans randomized to the control arm with psychoeducational materials (i.e., a list of suggested readings) that will also be received by the intervention arm. Control

arm participants will receive the psychoeducational materials in the same week that the intervention arm is scheduled to begin RECLAIM. Psychoeducational materials will be sent to the intervention and control arm using unencrypted email. Use of unencrypted emails for sending these materials has been approved by the Roudebush VAMC Privacy Office (see PO Request document).

Aim 2 Procedures:

A subset of participants from the intervention arm of the Aim 1 pilot study (n=16) will be invited to complete a single, individual qualitative semi-structured program experience and impact interview. Selection: Participants will be purposively sampled to take part in a qualitative interview based on their RECLAIM participation (i.e., participants who attended the most and fewest sessions). In each of the four cohorts, we will invite four participants to participate in a qualitative interview. This will provide a sample size of 16 interview participants. This sample size is consistent with published recommendations and our own experience to achieve saturation (i.e., when additional data do not provide new insights).⁴²⁻⁴⁵

Aim 3 Procedures:

At the conclusion of each study pilot cohort, the project team will review and refine the protocol manual. As we complete these iterative refinements, we will consult with the Patient Advisory Council of the Indianapolis VAMC (see letter of support) to gather Veteran feedback on the revised RECLAIM protocol manual. In addition, we will consult with partners from the VA Office of Patient Centered Care and Cultural Transformation and the Indianapolis Military 2VA Case Management Team (see letters of support). Refining the methods, design, and RECLAIM intervention will prepare us to submit a fully powered Hybrid Type I randomized controlled trial (RCT),²⁹ which we plan to submit as a HSR&D Investigator Initiated Research (IIR) Merit grant application.

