7.0 Data Collection & Storage

Aim 1 Data Collection:

Data will be collected to assess feasibility of screening, recruitment, randomization, and retention. We will also assess intervention engagement, treatment fidelity, and administration and completion of the outcome measures. These are described in greater detail below.

Intervention engagement: We will measure three indicators of participants' engagement with the intervention: (1) attendance at RECLAIM sessions; (2) attendance at optional check-in sessions; and (3) amount of independent/at-home practice. To assess independent/at-home practice, all participants randomized to the RECLAIM intervention arm will be provided an electronic mindfulness practice log sheet at the start of the study to track their engagement. Specifically, between RECLAIM sessions, participants will be asked to record how many days in the past week and approximately how many minutes per day they practiced mindfulness. They will also be asked to document any successes or difficulties that occurred. Practice log sheets will also ask participants to indicate how often they access the VA-approved cloud-based file storage application (e.g., Box) to use intervention materials (e.g., scripts, recordings). [Note: The VA-approved cloud-based file storage application will allow participants to access and download materials. The application will not allow participants to revise materials, upload their own materials, or provide any personal information (i.e., this application will not be used for data collection).] The practice log sheet can be completed electronically, or participants can print their log sheets to be completed manually. Participants can submit their practice logs to a member of the study staff via email. Additionally, at the beginning of each RECLAIM session, we will provide an electronic survey within the teleconferencing software that will match the questions/prompts on the participants' practice logs. This will provide participants another opportunity to submit their mindfulness practice information if they have not done so by email.

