Practice feedback: At the start of each weekly session, we will engage in a discussion about participants' independent practice (e.g., successes and challenges) and engage in discussion on strategies to maximize facilitators and overcome barriers. We will do weekly reminder calls to make sure participants are completing their logs and this will be another opportunity to provide any additional information or feedback to assist participants' independent mindfulness practice.

Treatment fidelity: Intervention fidelity has been defined as the degree to which an intervention was delivered as conceived and planned.⁴⁶⁻⁵⁰ Fidelity of the RECLAIM intervention will be evaluated by the Principal Investigator (PI), [name], who will be co-facilitating the RECLAIM sessions, and the Project Manager, who will observe the eight RECLAIM sessions across all four cohorts. Fidelity will be assessed using a checklist, which will be iteratively refined throughout the Aim 1 pilot. The checklist will capture intervention content elements (e.g., presentation of reintegration challenges,

mindfulness practices), as well as unplanned components (e.g., discussion questions and participant responses). The fidelity checklist for RECLAIM will facilitate the larger prepare for the planned Hybrid Type I trial,¹¹¹ which will assess the effectiveness of RECLAIM while simultaneously planning for implementation.

Administration of outcome measures: Part of our feasibility assessment will be to determine the acceptability of measures administered, time for outcome measure completion, number of items missing, and follow-up rates. We will administer assessments after a Veteran has consented to study participation to measure (1) depression, (2) general difficulty adjusting to civilian life, (3) anxiety, (4) quality of life, (5) mindfulness, and (6) pain. Participants will complete outcome assessments at two timepoints: baseline and 2-month follow-up. Participants will receive a \$25 gift card for each outcome assessment they complete, for a possible total of \$50.

1. **Depression severity:** The Patient Health Questionnaire (PHQ-9) is a reliable and valid 9-item measure of depression severity used to screen, diagnose, monitor, and measure the severity of depression.³⁶ It is one of the most widely used, reliable, and validated measures of depressive symptoms.³⁶

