2. **General difficulty adjusting to civilian life:** The Military to Civilian Questionnaire (M2C-Q) is an empirically validated self-report scale that measures general difficulty in readjusting to civilian life by assessing important indicators of reintegration challenges over the past 30 days including social/health behaviors, specifically interpersonal relationships; productivity at school, work, or home; community participation; self-care; leisure; and perceived meaning in life.³⁷ Research supports the construct and factor validity of scale scores and indicates high internal consistency (Cronbach's alpha = .92).³⁷
3. **Anxiety:** The Generalized Anxiety Disorder Scale (GAD-7) is a brief 7-item measure for assessing generalized anxiety disorder.⁵¹ The GAD-7 uses some of the Diagnostic and Statistical Manual of Mental Disorders (DSM-V) diagnostic criteria to assess generalized anxiety disorder. Scores classify respondents as having minimal, mild, moderate, or severe anxiety. The GAD-7 has good reliability and validity.⁵¹
4. **Quality of life:** The Veterans RAND Health Survey (VR-12) is a brief, self-administered health survey primarily used to measure health related quality of life.⁵²⁻⁵⁴ The VR-12 is one of the most widely used functional status measures and has been shown to be highly reliable and valid.⁵²
5. **Mindfulness:** The Five Facet Mindfulness Questionnaire (FFMQ) is a 15-item scale to measure five factors of mindfulness: (1) Observing; (2) Describing; (3) Acting with awareness; (4) Non-judging of inner experience; and (5) Non-reactivity to inner experience.⁵⁵ The FFMQ has strong psychometric properties, including good reliability for all facets (i.e., aspects) of mindfulness.^{37,56,57}
6. **Pain:** The PEG (pain intensity, interference with enjoyment of life, interference with general activity) is an ultra-brief measure that contains 3 items to assess pain levels on average, pain interference with enjoyment of life, and pain interference with general activity.⁵⁸ The PEG demonstrates strong reliability and validity.

Aim 2 Data Collection:

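### Could the single two-month follow-up, which has no stated starting point, fall before the eight-week programme ends?

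*Combined protocol and SAP*

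**What the plan says.** All of this is in the combined protocol and SAP.

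- **Order of events (section 6.0, Randomization).** "After completing the informed consent and baseline assessments, Veteran participants will be randomized to one of two study arms".
- **Start of the programme (section 6.0, Intervention arm).** Veterans in this arm "will participate in the 8-week RECLAIM intervention after 12 Veterans (i.e., a cohort) have been randomized". The programme has four group sessions and four coaching calls, and "The bi-weekly coaching calls will happen in the weeks between the virtual intervention sessions".
- **Control arm (section 6.0).** Control "arm participants will receive the psychoeducational materials in the same week that the intervention arm is scheduled to begin RECLAIM".
- **Follow-up (section 6.0, Aim 1 Procedures).** "These assessments will be completed again at the 2-month follow-up". Section 7.0 repeats it: "Participants will complete outcome assessments at two timepoints: baseline and 2-month follow-up". Neither place gives a starting date or a window.
- **Recall period (section 7.0).** The M2C-Q is described as "assessing important indicators of reintegration challenges over the past 30 days".
- **Analysis (section 8.0).** Feasibility is reported as counts and percentages. Outcome data are explored only for trends. No between-arm test of outcomes is described.

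**The concern.** Baseline and randomisation happen Veteran by Veteran, but nothing is delivered to either arm until 12 have been randomised. The first Veteran in a cohort may therefore wait some time, while the twelfth hardly waits at all. If the two months were counted from baseline, early entrants would be assessed with the programme unfinished, or even before it began, and members of one cohort would have had different exposure at follow-up.

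Three outputs would be affected. Retention in both arms and follow-up completion are Aim 1 measures, and without a window it is unclear when a follow-up counts as late or missed. Outcome trends meant to inform a larger trial would mix unequal intervals. Veterans lost while the cohort fills would not be told apart from those lost after delivery begins. For the intervention arm, section 7.0 records engagement as "1) attendance at RECLAIM sessions; (2) attendance at optional check-in sessions; and (3) amount of independent/at-home practice", so a Veteran who never starts would show up there; nothing similar is described for controls.

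**Working it through.** **Inputs from the documents.** N = 48 (section 2.0); cohorts of 12 and a programme of 8 weeks (section 6.0); follow-up at 2 months (sections 6.0 and 7.0); study length about 18 months (section 14.0).

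**Cohort structure.** 48 / 12 = 4, which agrees with the four cohorts named under Aim 2 Procedures. The 12 therefore count both arms together.

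**Slack.** The programme lasts 8 × 7 = 56 days. Two months = 2 × 365.25 / 12 = 60.9 days, so the slack is 60.9 − 56 = 4.9 days. By calendar, two months are 59 to 62 days, giving 3 to 6 days; read as eight weeks, the slack is 0.

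**Clock started at baseline or randomisation.** The programme day at follow-up is 60.9 − wait. The documents give no accrual rate, so the fill time T is an assumption. With even accrual and no gap after the twelfth randomisation, the i-th Veteran waits T(12 − i)/12. If delivery starts in week 1 (also an assumption), the last coaching call is on day 49 and the last of four fortnightly group sessions on day 42.

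| Assumed fill time T (months) | 0.5 | 1.5 | 2.25 | 3 |
|---|---|---|---|---|
| Longest wait (days) | 14.0 | 41.9 | 62.8 | 83.7 |
| Of 12, assessed before day 56 | 8 | 10 | 11 | 11 |
| Of 12, before day 49 | 2 | 8 | 9 | 10 |
| Of 12, before day 42 | 0 | 7 | 8 | 9 |
| Earliest programme day at follow-up | 46.9 | 19.0 | −1.9 | −22.8 |

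The study length gives only an upper bound on the average fill time: (18 − 2)/4 = 4.0 months, with nothing set aside for set-up or close-out.

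For nobody to be early on this clock, the first Veteran's 11 gaps must fit into 4.9 days. That needs 11 / 4.875 × 30.44 = about 69 randomisations a month, more than the whole sample of 48. A baseline clock would thus almost always defeat the purpose of the visit.

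**Clock started at the cohort's first week.** Everyone is assessed at day 60.9 from the start, 4.9 days after the programme ends (3 to 6 by calendar). The number assessed early is 0 of 12 at any fill time. The interval from baseline to follow-up is 2 months plus the wait, so its longest value is 2.46, 3.38, 4.06 or 4.75 months for the four fill times. A clock started at programme end also leaves nobody early.

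**Age of the baseline at the start.** On any clock, 0, 4, 6 or 8 of 12 baselines would be more than 30 days old. Two of these counts sit on the boundary: with a 30-day month they become 0, 3, 6 and 7.

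**Which clock the text supports.** The programme lasts eight weeks and the single follow-up comes at about that distance. Control materials are tied to the cohort's first week, so both arms share one start. Interview invitations and manual revisions are also organised by cohort. These points all favour cohort start, and nothing in the text favours baseline.

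**The case for a change.** The strongest case for a change is that the anchor really is absent, that writing it down would take one sentence, and that a pilot reporting follow-up completion as a percentage should say when a follow-up is on time. The wait is itself part of the group design being tested, and the retention measures built around sessions (recap emails, reminder calls) do not reach Veterans who are still waiting.

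The omission stands. The consequence does not follow from it. Early assessment arises only on a clock that the text does not favour, and its size rests on assumed accrual. The count before the last group session also depends on the delivery calendar. Section 6.0 describes four fortnightly sessions, while section 7.0 (Treatment fidelity, Practice feedback) speaks of eight sessions and of weekly ones. With eight weekly sessions the last falls on day 49, and the counts 0, 7, 8, 9 become 2, 8, 9, 10. Those passages must be reconciled, but that is a separate matter: on the cohort-start clock follow-up comes after day 56 either way.

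The other remedies gain little. Naming an anchor leaves the age of the baseline as it was. Splitting losses by date works for dated withdrawals, but a control who goes silent cannot be placed before or after the start without a contact that the plan does not describe. Taking baseline and randomising just before the start would give fresher baselines, but consented Veterans would have to be held and contacted again, and the losses during the wait would move to before randomisation without disappearing.

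**Conclusion.** No change is needed. The missing anchor and window are details that a team scheduling visits by cohort would settle sensibly, and the natural reading puts follow-up about 4.9 days after the eight weeks for every Veteran in both arms. This rests on counting from the cohort's first week, which the common start of the two arms supports but which is not stated.

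What is left is a baseline of varying age. The documents give no accrual rate from which to size it; under the assumed fill times the longest interval from baseline to follow-up is about 2.5 to 4.75 months. Both arms wait alike, so no between-arm bias arises. No power figure depends on it, and the outcome results are descriptive. Assessing Veterans before the cohort fills is a fair trade-off in a group-delivered pilot.
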